6.2 ENROLLMENT VISIT

6.2.1 Enrollment for HIV seronegative participants initiating PrEP

Enrollment will occur following determination of study eligibility and after completion of full study consent. This visit may occur up to 7 days following eligibility determination. A participant will be considered enrolled after completing all informed consent activities, including randomization. All enrolled participants initiating PrEP will have undergone HIV antibody testing in accordance with local PrEP eligibility determination processes. As part of study participation, they will be evaluated for acute HIV infection with HIV RNA testing (see [Section 9.1](#)). Persons with any detectable HIV RNA from enrollment visit will be linked to appropriate HIV care. They will remain in the study for a maximum of an additional 26 weeks following seroconversion to facilitate additional testing and confirm viral suppression on antiretroviral therapy.

In both control and intervention arms, we will capture in-depth behavioral and health assessments, using validated scales where possible to facilitate exploration of predictors of PrEP persistence and inform specific objectives and strategies to improve psychosocial counseling interventions. To obtain more granular information regarding sexual activity, particularly relevant for cisgender men who choose event-driven oral PrEP, we will use a timeline follow-back (TLFB) in which self-reported sex acts over the past 30-days are captured in a calendar format.

Administrative, Behavioral, and Regulatory Procedures:

- Informed consent
- Locator information
- Behavioral risk, risk perceptions, and 30-day health assessment
 - timeline follow-back (TLFB; sex acts)
 - substance use
 - mental health
 - anticipated and experienced PrEP-related stigma
 - anticipated and experienced HIV-related stigma
 - gender norms
- PrEP use assessment*
- HIV risk reduction counseling

**The PrEP use assessment is a basic assessment of if the individual is using PrEP, self-reported adherence, and other related factors.*

Clinical Procedures:

- Symptom-driven physical examination
- Blood collection
- Urine collection

Laboratory Procedures:

- HIV rapid antibody testing
- HIV RNA
- Chlamydia trachomatis/Neisseria gonorrhoeae (CT/NG)
- Syphilis testing (RPR & reflex TPPA if appropriate)
- Plasma storage
- Urine storage
- Dried blood spot (DBS) storage

6.3 FOLLOW-UP VISITS

Study specific assessments will be conducted separately from STI-clinic based PrEP visits. The proposed study duration is approximately 15 months (65 weeks) total, with individual participants being followed on study for at least 26 weeks and up to 52 weeks, depending on the time at enrollment. Recruitment will be conducted within approximately 39 weeks.

Any participant who has had a reactive/positive HIV test during PrEP follow-up will have further testing to confirm infection. In all cases, confirmation of infection requires testing samples collected on two different dates.

In both control and intervention arms, study specific visits will be conducted as follows:

6.3.1 Quarterly visits (Weeks 13, 26, 39* and 52*)

The following procedures will be conducted at each quarterly visit:

Administrative and Behavioral Procedures:

- Locator information (if location has changed)
- Behavioral risk, risk perceptions, and health assessment
 - 30-day timeline follow-back [TLFB] (sex acts and PrEP use)
 - substance use
 - mental health
 - anticipated and experienced PrEP-related stigma
 - anticipated and experienced HIV-related stigma

- gender norms
- PrEP use assessment
- HIV risk reduction counseling

Clinical Procedures:

- Symptom-driven physical examination
- Blood collection
- Urine collection

Laboratory Procedures:

- HIV rapid antibody testing
- Syphilis RPR & reflex TPPA if appropriate
- CT/NG (if >2 weeks since testing conducted at PrEP visit)
- Plasma storage
- Urine storage
- DBS storage

**A subset of participants will also have a visit at Weeks 39 and 52, if the window of study follow-up allows. Participants enrolled in the first 13 weeks of recruitment will be followed for 52 weeks and those enrolled during the first 26 weeks of recruitment will be followed for 39 weeks. The remaining participants will be followed for 26 weeks total follow-up.*

Identical procedures will occur at Weeks 13, 26, 39, and 52, with the notable exception that a subset of participants will be asked to engage in an in-depth interview during their final visit (Week 26, 39, or 52).

6.4 PROCEDURES FOR PARTICIPANTS WITH SUSPECTED OR CONFIRMED HIV INFECTION

The following sections relate specifically to HIV seronegative participants initiating PrEP.

6.4.1 Enrollment

HIV testing will be performed to identify persons with HIV infection prior to enrollment, in line with Malawi PrEP eligibility and HIV testing guidelines ([Section 4.3](#)). Individuals who have one or more reactive/positive HIV tests at eligibility assessment (prior to enrollment) are not eligible to participate in this study as PrEP participants. Per current Malawi PrEP eligibility criteria ([Section 4.1](#)), PrEP should not be offered to persons with signs or symptoms consistent with acute (pre-seroconversion) HIV infection. All enrolled HIV-seronegative participants will be screened for acute HIV infection with HIV RNA testing ([Section 9.1](#)), regardless of signs or symptoms, as part of study procedures. Persons with detectable HIV RNA from enrollment visit will be linked to appropriate HIV care and followed as described in [Section 6.1](#).

6.4.2 After study enrollment

Participants will be tested for HIV at all follow-up PrEP visits prior to distribution of PrEP medication, per Malawi standards. Participants will be tested for HIV at all study visits, regardless of HIV testing results from PrEP visits. Participants who have any reactive/positive HIV test result during follow-up visits will be referred for care. These participants will have further testing to confirm infection and will be followed quarterly up to approximately 26 weeks to assess viral suppression. In all cases, confirmation of infection requires testing samples collected on two different dates.

6.5 OTHER STUDY PROCEDURES

6.5.1 Sexually transmitted infections

Testing for CT/NG and syphilis will occur throughout the study. Testing will be performed at LL. Intervention arm participants who have been tested within the two weeks prior to a study visit as part of their PrEP care will not be re-tested for CT/NG. Syphilis testing may be repeated as the PrEP clinic uses POC tests that are not entered into Laboratory information systems and thus cannot be captured other than self-report/paper medical record. POC test results documented in participant records may be extracted using case report forms, however, all CT/NG and syphilis results performed at LL will be entered into appropriate study databases, extracted from existing laboratory information systems. Results will not be returned same day, however, participants who test positive for an STI at study visits will be informed of their result and be referred for treatment as per local guidelines.

6.5.2 HIV and risk reduction counseling

PrEP visits: Participants randomized to the standard of care arm who remain engaged in PrEP care will receive HIV testing and counseling, as well as any risk reduction counseling, from MoH staff and PrEP nurses (respectively) in accordance with local policy and guidelines. Participants randomized to the intervention arm will similarly receive HIV testing and counseling and PrEP counseling from MoH staff, as well as relevant counseling through systems navigation.

Study visits: Standard pre- and post-test counseling will be provided as part of HIV testing conducted at each study visit (see [Section 6.3](#)). All participants will be offered condoms.

6.6 QUALITATIVE DATA COLLECTION

To assess the acceptability of the intervention, individual semi-structured interviews will be conducted with stakeholders, including enrolled participants (during final study visit), and other clinic-based key stakeholders who will be engaged during the final stages of intervention follow-up. Stakeholders include key personnel as described in [Section 4.1](#).

Participation of all stakeholders will be entirely voluntary. The subset of PrEP user participants will assent and/or consent to participate in their enrollment consent, but can

opt out upon being approached for an interview. If other stakeholders choose not to participate, he/she will experience no penalty or loss of employment or benefits. Procedures will be undertaken to ensure that no penalties are incurred nor pressure exerted by supervisors. The informed consent process for interviews will be conducted in a location that assures adequate privacy and confidentiality.

All interview transcripts will be stripped of personal identifiers. Reports and publications will be thoroughly redacted to confirm that no identities can be discerned.

Semi-structured interviews will follow a standard guide that includes probes and queries specific to stakeholders. They will explore experiences with the intervention, perceived barriers to persistent PrEP engagement among the target population, and potential barriers or facilitators to scaling or sustaining the intervention. Specifically, interviews will explore how the intervention successfully or unsuccessfully addresses barriers or enhances facilitators of PrEP uptake and persistent effective use. Barriers will be also assessed through the barrier questionnaire with the participant systems navigators' data forms/log books, and interviews with additional stakeholders.

All interviews will be audio-taped, translated, and transcribed by qualified personnel, with any identifiable information redacted from transcripts prior to dissemination for analysis.

6.7 COST AND RESOURCE DATA COLLECTION

We will embed empirical costing into study procedures. Costs will be collected prospectively in two ways: micro costing and time-and-motion logs. Micro-costing involves "direct enumeration" for consumed inputs, an ingredients-based approach. We will quantify resources associated with the development and implementation of our intervention. We will also extract data from project expenditure and management records, including purchase logs and human resource records. Time-and-motion assessments record how involved parties (navigators) divide time among navigation-related tasks, reliably apportioning effort relevant to implementing the intervention. This includes time for trainings, counseling, tracing, and other related tasks. No formal modeling is proposed as part of this protocol.

6.8 VISIT WINDOWS

For each required study visit, there is an allowable visit window specifying on which study days (post-enrollment) the visit is "allowed" to be completed. The allowable visit windows are contiguous from visit to visit, and do not overlap. Within each allowable visit window, there is a target visit window and study visits should ideally be conducted within this window. These windows are outlined in the table below. If more than one visit is necessary to complete all visit procedures, these could be completed during multiple days within the allowable visit window.

Table 1. Visit Window Schedule

Visit	Target Visit Day	Target Visit Window	Target Visit Window Days	Allowable Visit Window
Eligibility Determination	--	--	Up to 7 days before enrollment	--
Enrollment	Day 0	--	0	0
Week 13	Day 91	-21/+21	Day 70 – 112	Day 70 - 153
Week 26	Day 182	-21/+21	Day 161 - 203	Day 154 - 244
Week 39 (optional)	Day 273	-21/+21	Day 252 - 294	Day 245 - 336
Week 52 (optional)	Day 365	-21/+21	Day 344 - 386	Day 337 – 427

6.9 INTERIM CONTACTS AND VISITS

Interim contacts and visits (those between regularly scheduled follow up visits) may be performed at participant request or as deemed necessary by the IoR or designee at any time during the study. All interim contacts and visits will be documented in participants' study records and on applicable CRFs.

Some interim visits may occur for administrative reasons. For example, the participant may have questions for study staff. Interim visits at which no data are collected are not documented on CRFs. Other interim contacts and visits may occur in response to social harms experienced by study participants. When interim contacts or visits are completed in response to participant reports of social harms, study staff will assess the reported event, record the event on the CRF, and provide or refer the participant to appropriate medical care.

7.0 MONITORING AND ADVERSE EVENT REPORTING

7.1 ADVERSE EVENT REPORTING

As this study only involves low-risk activities (recruitment activities; testing for HIV and STIs; questionnaires; support for linkage-to-PrEP, PrEP engagement, and PrEP adherence) and contains no biomedical intervention or clinical care (PrEP prescription or other medical treatment), standard adverse event reporting and monitoring will not be undertaken. Any product related to this study (i.e. PrEP) is not being offered or administered directly by the study staff. All drugs used by participants in this study (i.e., PrEP, STI treatment) for the prevention of HIV or management of STIs, have regulatory approval for this purpose in Malawi and have well-established safety profiles. All safety monitoring of these approved drugs will be at the discretion of Malawi Ministry of Health.

Confidential HIV and STI surveillance reporting will be done according to local regulations. Participants will be reminded of these requirements via the Informed Consent Form.

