Fluctuations in oral PrEP also expose patients to HIV risk.¹⁷ As such, our study design integrates a “return-to-PrEP” kit, including a 14-day supply of oral PrEP and a home HIV test kit for participants who, after counseling sessions, decline interest in additional PrEP. Participants who no longer feel they need PrEP are encouraged to return to the PrEP clinic and are offered this “re-start” kit alongside instructions for self-testing and use of the pill pack to facilitate immediate protection if they are not able to plan far enough to restart PrEP in a timely manner. This “re-start” kit will be provided by systems navigators (see [Section 5.4](#)).

Our STI-clinic based recruitment approach capitalizes on the synergistic co-STI/HIV epidemics globally and in the region and population of interest. Findings could inform a multi-site/multi-country implementation science study in which systems navigation is integrated into STI clinics as a strategy to recruit and retain high-risk heterosexual cisgender men in effective HIV prevention tools, including PrEP.

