5.0 STUDY INTERVENTION PACKAGE

The study intervention components, as described below, are integrated into the PrEP visit for participants randomized to the intervention arm. Timing for PrEP visits will be determined by the MoH PrEP nurse, aligning with contemporary recommendations for PrEP follow-up. According to the Malawi Ministry of Health PrEP program, persons who initiate oral PrEP are scheduled for PrEP follow-up visits at months 1, 3 and every 3 months thereafter. Injectable PrEP guidelines are not yet available but are expected to include a visit at 1-month and then every two months thereafter, aligning with scheduled

injections. The study intervention will not interfere with regular PrEP care – PrEP nurses will still proceed with any PrEP adherence counseling as well as any HIV risk reduction counseling consistent with Malawi PrEP guidelines at each PrEP visit.

The study intervention package includes: 1. Access to a systems navigator, intended to engage with participants at each PrEP visit and who can trace participants who do not attend a scheduled PrEP visit; 2. POC STI testing; and 3. A PrEP re-engagement or “re-start” kit offered to participants who choose to stop PrEP.

Study intervention activities occur primarily at the Bwaila STI clinic, with the notable exception of tracing for missed visits, which fundamentally will occur in the field. PrEP visits, and any associated meetings with systems navigators, will occur at the Bwaila STI clinic, whereas HPTN 112 study visits (conducted by non-navigator study staff), will occur in a separate building. The schedule and content of study visits is further specified in Section 6.3, and occur quarterly regardless of a participants’ ongoing PrEP use or PrEP schedule.

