5.4 PREP RE-ENGAGEMENT AND “RE-START”

For participants who choose to discontinue PrEP, navigators serve as a point of contact for re-engagement and will encourage participants to re-initiate PrEP if or when HIV risk resumes. It is expected that most participants who choose to discontinue PrEP will not attend their scheduled PrEP visit, and thus the decision to discontinue PrEP will often be identified at the point of navigator-initiated tracing (see above). Any participant who discontinues PrEP will be offered a PrEP “re-start” kit, which include a supply of oral PrEP, an HIV-self test, and brief instructions to facilitate safe immediate restart in the event that risk recurs without their first re-engaging in clinic-based PrEP care. Acceptance and use of this kit will be explored in subsequent study visits.

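### Section 7.1 waives adverse event reporting partly on statements that fit poorly with the navigator-provided PrEP re-start kit, and no safety report is tied to kit use

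*Protocol*

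**What the plan says.** Protocol Section 7.1 gives several grounds for not undertaking standard adverse event reporting:

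- The activities are low risk. The list covers recruitment, HIV and STI testing, questionnaires, and support for PrEP linkage, engagement and adherence. The re-start kit is not on it.
- The study "contains no biomedical intervention or clinical care (PrEP prescription or other medical treatment").
- "Any product related to this study (i.e. PrEP) is not being offered or administered directly by the study staff".
- The drugs are approved in Malawi with established safety profiles, and their monitoring is left to the Ministry of Health. Section 3.0 adds that the study will do no further PrEP safety monitoring to inform care.

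The kit is described elsewhere:

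- Section 1.2 describes it as "including a 14-day supply of oral PrEP and a home HIV test kit for participants who, after counseling sessions, decline interest in additional PrEP". It comes "alongside instructions for self-testing and use of the pill pack", and the "kit will be provided by systems navigators".
- Section 5.0 makes it the third component of the study intervention package, a "kit offered to participants who choose to stop PrEP".
- Section 5.4 says that it is meant to allow "immediate restart in the event that risk recurs without their first re-engaging in clinic-based PrEP care".

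**The concern.** A waiver of safety reporting should rest on statements that hold for everything the study does. Two of the statements in 7.1 are hard to square with a randomised component in which a navigator hands over antiretroviral pills.

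The delegation to the Ministry also fits kit use poorly. Under Section 6.4.2, a man at a PrEP visit is tested for HIV before medication is distributed. With the kit, the self-test stands in for that clinic test, and the pills may be started before any contact with Ministry PrEP care.

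What is at stake is practical. If a man falls ill or has a reactive self-test after using the kit, the protocol should say plainly whom he tells and where the event is counted. A larger trial would also want those counts. The primary comparison of PrEP persistence is not affected.

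**Working it through.** The point is textual, so the check sets the sections side by side. The only arithmetic concerns timing and scale.

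**1. Does the study contain a drug component?** Section 5.0 places the kit in the study intervention package, and Section 1.2 says that it holds 14 days of oral PrEP. Section 7.1 glosses its denial as prescription or other medical treatment. The men were prescribed PrEP before enrolment (Section 4.1), and Section 3.0 assigns all PrEP services to the Ministry. The protocol does not say who prescribes or stocks the kit's pills. If the Ministry does, the conflict narrows. The kit would still be a study component that delivers drug.

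**2. Are navigators study staff?** Usage is mixed.
- For: Section 5.0 describes study visits as "conducted by non-navigator study staff", which implies that navigators are study staff too. Section 7.3 counts navigators among all staff, and an Appendix II footnote treats navigation as provided by the study.
- Against: Section 3.0 separates navigators from the staff who trace missed study visits. Section 10.3 assigns the two kinds of tracing to study staff and navigators respectively. Section 4.3 has study staff approach and enrol men before navigators engage them.

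The sentence in 7.1 could therefore be read as literally true, but only on a narrow reading that 7.1 does not state.

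**3. Which safeguards reach a kit user?**
- Investigator evaluation of safety information, emergency-care advice and possible ad hoc Study Monitoring Committee (SMC) review (7.2).
- Further testing after a reactive test (6.3), HIV testing and symptom-driven examination at quarterly visits (6.3.1, 6.4.2), and testing on an expressed concern (9.3).
- Interim visits on request (6.9), and navigator contact and kit instructions (1.2, 5.2, 5.4).
- Reports of unanticipated problems to ethics bodies (10.1).

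All of these are general except the kit instructions, and those are not a reporting route.

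**4. What is recorded about the kit?** Section 5.4 says that acceptance and use will be explored at study visits. Section 8.2.1.2 has three self-reported endpoints: use of the self-test, use of the pill pack, and use of the self-test with or before the pills. The protocol does not specify recording of the test result, illness after use, or linkage to care. In Section 7.2 the 24-hour number is given for social harms, and the routine SMC reports cover study conduct and social harms.

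**5. Timing and scale** (Sections 6.8, 7.2, 8.1).
- Target gap between the week 13 and week 26 visits: 182 − 91 = 91 days.
- Within the target windows, shortest gap: 161 − 112 = 49 days. Longest gap: 203 − 70 = 133 days.
- The 14-day supply is shorter than 49 days, so a course can start and finish between two scheduled study visits that are both on target. This says nothing about how often harm would occur.
- Men who could be offered a kit: 200 × 2/3 ≈ 133. The number who will be offered one cannot be derived from the protocol.
- Routine SMC reviews: 65 weeks ÷ about 26 weeks = 2.5, so about two.

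**The case against.** The strongest reply is that 7.1 is defensible as worded. Several sections treat navigators as separate from study staff, the gloss in 7.1 is about prescription, and prescription belongs to the Ministry. This stands in part. It means that the statements cannot be called plainly false, only that they fit poorly with the kit.

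A reader might infer that the protocol hides drug provision from its reviewers. It does not. The kit appears in the schema, in Sections 1.2, 3.0, 5.0 and 5.4, and among the endpoints, and ethics bodies review the whole protocol.

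A reader might also infer that a kit user has no safety cover. That is not supported either: the safeguards listed above apply to him, including a symptom-driven examination and an HIV test at each quarterly visit.

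Finally, the kit instructions, navigation manual and case report forms are not shown, and they may already ask for the missing items. This limits the third part of the fix, which is conditional for that reason. It does not answer the mismatch within the protocol's own text: 7.1 omits the kit, and the delegation to the Ministry does not fit use outside clinic care.

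**Conclusion.** The point holds at minor severity. Two of the grounds in 7.1, and its delegation of drug monitoring, fit poorly with the re-start kit. The protocol's provisions for problems after kit use are general, and no safety report is tied to the kit.

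It might be inferred that the waiver falls and that full adverse event reporting is required. The documents do not support this. The approved-drug and low-risk grounds remain, and the men had been cleared for PrEP before enrolment. No endpoint, test or sample size changes.

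Two things could narrow the conclusion: Ministry prescription or supply of the kit drug, and working documents that already capture the three missing items. Neither can be settled from the protocol.

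**What to change.** 1. In 7.1, add the re-start kit to the list of activities. State that navigators provide 14 days of approved oral PrEP with an HIV self-test in the intervention arm, and rest the waiver on the approved-drug and low-risk grounds.
2. In 7.2, state that the existing 24-hour number also takes reports of illness or of a reactive self-test after kit use.
3. Unless the case report forms already do so, add three items to the kit-use questions at the existing quarterly visits: self-test result, illness or medical attention after use, and linkage to care if reactive. Give the counts in the routine SMC report.

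The cost is a protocol amendment. Section 11.5 requires approval by the Protocol Chair, the DAIDS Medical Officer, the ethics bodies and the Regulatory Support Center, and Section 11.1 requires an amendment registration packet. Beyond that, there are up to three form items and one table in about two routine reports, with no new visits or staff. The added data would be self-reported and come from the intervention arm only, so they would have no standard-of-care comparison.
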